5 STUDY AGENT

5.1 Study Agent, Storage, and Stability

oAC will be obtained as Actidose Aqua® (Paddock Laboratories), which is sold "over the counter" in the United States in bottles containing 25 g/120 mL (NDC # 0574-0121-04) or 50 g/240 mL (NDC # 0574-0121-08). oAC is stable at room temperature. For further information, see Package Insert (Appendix 3) and Drug Safety Sheet (Appendix 4).

AS will be obtained from Guilin Pharma (Shanghai), the only pharmaceutical company GMP pre-qualified by the WHO. The product 'artesunate for injection + 5% sodium carbonate inj + 0.9% sodium chloride inj' will be delivered in 60-mg vials and will be dosed at 2.4 mg/kg as recommended for SM treatment by the WHO (1).

Amodiaquine will be obtained from Pfizer (Dakar), is provided as 200-mg tablets or syrup (10 mg/mL), and will be provided as age-based doses per the manufacturer's directions.

5.2 Preparation, Administration, and Dosage

Considering that oAC is an inert substance that is not absorbed from the gut, we estimated a human dose equivalent to the 2.6 mg dose we used in a 20 g mouse (32), based on the ratio of calculated gut volumes. Chivers et al. established linear relationships (v = mx + c) between log gut volume (x) and log bodyweight (y) for faunivore, frugivore, and folivore primates (39), and we used the mean values for constants m (slope) and c (intercept) reported in these three equations to develop an equation for gut volume for omnivore primates. Gut volumes calculated for different human body weights were divided by the calculated mouse gut volume to derive a factor by which the mouse 2.6 mg dose was to be multiplied. Chivers et al. give error bounds for the constant m based on 95%Cls, and since intestinal volumes may vary depending on food intake (40), we have introduced an error term of $\pm 2SE$ for constant m. We propose to test the dose calculated from the equation, m + 2SE (Table 1). These oAC doses are well within the range of doses recommended for the treatment of acute poisoning: 1 g/kg in children aged <1 year and 25-50 g in children aged 1-12 years (30). Since intestinal transit time in African pupils from a semi-urban area is about 18 h (41), and both the efficacy of oAC to prevent ECM and treat poisoning is enhanced by repeat dosing (32, 42, 43), we will administer oAC on admission and 6, 12, and 18 h later. Actidose Aqua® (in the oAC plus AS group) or an equivalent amount of clean water for the control group will be given at the following weight-based doses:

Body	Dose (g)	Actidose-
weight (kg)	_	(mL)
6	4.3	20.7
8	6.3	30.1
10	8.4	40.2
12	10.6	50.9
14	13.0	62.2
16	15.4	74.0
18	18.0	86.2
20	20.6	98.9
22	23.3	111.9
24	26.1	125.4
26	29.0	139.1
28	31.9	153.2
30	34.9	167.5
32	38.0	182.2
34	41.1	197.1
36	44.2	212.3
38	47.5	227.8
40	50.7	240.0

Table 1. oAC dose by body weight, derived using formulae in Chivers et al.(39).

Actidose Aqua® will be administered PO at 0, 6, 12, and 18 h. Actidose Aqua® is licensed for use in infants and children at single or multiple doses of 25-50 g (120-240 mL) in children 1-12 years old. In multiple-dose regimens, doses are administered 4 to 6 h apart. The doses and dosing schedule proposed here are well within the licensed ranges. Per manufacturer's directions, the bottle will be shaken for 30 sec prior to opening and the appropriate volume

measured in a beaker. There are no absolute contraindications to the use of Actidose Aqua®. Side effects may include mild transient constipation and stools will be black for several days. If a child vomits within 60 min of taking any dose of oAC or water, the child will be withdrawn from the protocol.

Table 2. Sample size scenarios for different inferiority margins

6.2 Analysis plan

Analysis of safety data:

The local reactogenicity at the site where the IV catheter is placed will be assessed using the grading scale provided in Appendix 5, which is based on the FDA toxicity grading scale for healthy adults and adolescents.

Descriptive summaries of the frequency and (where applicable) duration of systemic signs and symptoms such as nausea, vomiting, diarrhea, abdominal pain, headache, and dizziness will be provided for each group.

Clinical and laboratory assessments resulting in numerical values (pulse, blood pressure, respiratory rate, state of consciousness assessed by the Blantyre coma score, axillary temperature, white blood cell counts, hemoglobin, and platelet counts) will be compared at each time-point between groups in light of age-specific normal values available for African pediatric populations (44-46).

It is expected that all the above listed parameters will be influenced to various degrees by the malaria parasite infection itself, and most of the systemic signs or symptoms are also listed as

common side effects of the antimalarial drugs used to treat the infection. Therefore, it won't be possible to establish the relatedness of any such findings to either the parasite infection, or any of the study-related interventions. For that reason, we will limit our analysis to a comparison of the frequency and duration (or, for numeric parameters the level) of such findings between both groups. This will enable us to determine whether adjunct treatment with oAC significantly alters the clinical course of disease, or whether the safety of IV AS is compromised by adding oAC.

Analysis of parasite clearance data:

Parasite clearance will be calculated for each participant as previously described (38), and compared between groups using a one sided test with a 2.5% significance level. The hypotheses are: H_0 : T_H for AS + oAC – AS >25.57 min and H_1 : T_H for AS + oAC – AS <25.57 min. The Welch's t-test will be performed and its associated 95% CI will be calculated for the mean difference between AS+oAC – AS. If the upper limit of this interval is <25.57 min, then the null hypothesis will be rejected and non-inferiority will be demonstrated.

The number/proportion of children who did not receive their last dose of oAC because their peak parasite density / 18-h parasite density was <2.0 will be reported in both groups, and their parasite clearance rates will be compared with the children who received the full course of oAC.

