We will hospitalize children for 48 h to monitor their clinical status and IV catheter, and ensure the accurate timing of blood sampling. Vital signs, state of consciousness, and selected symptoms (nausea, vomiting, diarrhea, constipation, abdominal pain, headache, and dizziness) will be monitored at 0, 2, 4, 6, 8, and 12 h, and then every 6 h until 48 hours or until parasitemia is undetectable (one negative thick blood film), whichever is later. Finger-prick blood samples will be obtained at 0, 2, 4, 6, 8, and 12 h, and then every 6 h until parasitemia is undetectable. In

Kenieroba, we previously found that 7%, 13%, 34%, 28%, 16%, and 2% of children aged 2-10 years (n=160) cleared their parasitemia by 12, 18, 24, 30, 36, and 42 h, respectively (38). We therefore expect that finger-prick blood sampling will be completed within 48 h for all children.

We will obtain 3 mL venous blood at 0, 24, and 48 h to perform a complete blood count (CBC) with differential and platelet counts, preserve RNA, and store plasma for research purposes. Transcriptional profiles and plasma cytokine levels in children with UM children will later be compared to those with SM.

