- 2. Measure vital signs, assess consciousness, and review specific symptoms. (i.e., nausea, vomiting, diarrhea, constipation, abdominal pain, headache, dizziness)

36 hours (±10 min)

- 1. Prepare thick and thin blood films and count parasite density. Slide readers will be blinded to study participant's group allocation.
- 2. Inspect IV catheter.
- 3. Measure vital signs, assess consciousness, and review specific symptoms. (i.e., nausea, vomiting, diarrhea, constipation, abdominal pain, headache, dizziness)

42 hours (±10 min)

- 1. Prepare thick and thin blood films and count parasite density. Slide readers will be blinded to study participant's group allocation.
- 2. Measure vital signs, assess consciousness, and review specific symptoms. (i.e., nausea, vomiting, diarrhea, constipation, abdominal pain, headache, dizziness)

48 hours (±10 min)

- 1. Prepare thick and thin blood films and count parasite density. Slide readers will be blinded to study participant's group allocation.
- 2. Inspect IV catheter.
- 3. Measure vital signs, assess consciousness, and review specific symptoms. (i.e., nausea, vomiting, diarrhea, constipation, abdominal pain, headache, dizziness)
- 4. Obtain 3 mL blood via IV catheter for research purposes.
- 5. Administer AS 2.4 mg/kg IV to all children.
- 6. Remove IV catheter.
- 7. If the parasitemia is undetectable, discharge participant from inpatient ward.

If parasitemia is detected at 48 h, we will retain the child as an inpatient, and continue preparing thick and thin blood films and counting parasite density until parasitemia is undetectable on thick smear in 6-hourly intervals.

Three age-based doses of AQ will be given orally on Days 4 (approx. 72 h), 5 (approx. 96 h), and 6 (approx. 120 h). On each day, we will record whether the child has passed stool.

On day 7 (approx. 168 h), we will follow up the participant to ensure (s)he is in good health. The site where the IV catheter was placed will be inspected, vital signs will be monitored, specific symptoms will be reviewed, and the outcome of any AE will be documented. At the discretion of the investigator, a focused clinical exam may be performed. A finger-prick blood sample will be

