8 POTENTIAL RISKS AND BENEFITS

8.1 Potential Risks

Potential risks to participants are associated with the following procedures:

Venipuncture and finger sticks. Risks occasionally associated with venipuncture include pain, bruising, bleeding, and infection at the site of venipuncture, lightheadedness, and rarely, syncope.

Indwelling venous catheterization. Risks rarely associated with the placement of indwelling venous catheters include line infection and venous thrombosis.

If the IV line becomes compromised and cannot be replaced, treatment will be continued with intramuscular artemether. In rare circumstances, intramuscular injection may cause infection of superficial and deep tissues, including muscle abscess. Inappropriate injection techniques may result in nerve damage that may be permanent.

Drug administration. Expected AEs of drugs used in this study are generally mild in nature and not treatment-limiting.

Repeat dosing of oAC may cause constipation, and stools may be blackened. Aspiration of oAC in patients who vomit has been reported to produce airway obstruction (which is one reason why children presenting with repeated vomiting will not be eligible). oAC can reduce the absorption of other oral medications for as long as it is present in the intestines. The effect is greatest when oAC is given simultaneously (i.e., within 1 h) with other oral medication, additional doses of which may be required to obtain the same clinical effect.

Gastrointestinal effects (nausea, vomiting, diarrhea, abdominal discomfort) have been noted with AQ treatment, but have been extremely uncommon in our study population in the past 5 years. Rarely, itching and skin rash may occur.

No AEs are expected from AS or artemether treatment. The drugs are well tolerated, and there are no known common side effects. Rarely, allergic reactions and skin rash have been described.

Study participants will be made fully aware that this is the first time that patients with malaria will receive adjunct treatment with oAC. While there is currently no evidence that oAC might do any harm, we cannot exclude the theoretical possibility that oAC may produce unexpected, less desirable outcomes.

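### The symptom review has no scheduled time between 48 h and about 168 h, and section 6.2 does not say how constipation and the Day 4-6 stool record will be summarised (minor)

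*Combined protocol and SAP*

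**What the plan says.** All references are to the combined protocol and SAP.

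- **Outcome.** Section 6.3.1 lists the safety of adjunct oAC as its first item, ahead of parasite half-life.
- **Expected effect of oAC.** Section 5.2: "Side effects may include mild transient constipation and stools will be black for several days". Section 8.1: "Repeat dosing of oAC may cause constipation, and stools may be blackened".
- **Dosing.** Section 5.2: "Actidose Aqua® will be administered PO at 0, 6, 12, and 18 h".
- **Symptom review.** Section 3.2: "selected symptoms (nausea, vomiting, diarrhea, constipation, abdominal pain, headache, and dizziness) will be monitored at 0, 2, 4, 6, 8, and 12 h". From that point the same section continues the review at wider intervals: "then every 6 h until 48 hours or until parasitemia is undetectable (one negative thick blood film), whichever is later". Section 7.1 repeats the same seven symptoms at each inpatient time point and schedules a further symptom review at about 168 h.
- **Days 4, 5 and 6.** At the amodiaquine contacts (about 72, 96 and 120 h), the only bowel or symptom item in 7.1 is: "On each day, we will record whether the child has passed stool".
- **Analysis.** Section 6.2 promises summaries of how often symptoms occur and, if applicable, how long they last: "systemic signs and symptoms such as nausea, vomiting, diarrhea, abdominal pain, headache, and dizziness will be provided for each group". It then limits the safety analysis to comparing such findings between the two groups.

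**The concern.** The safety comparison depends on how often symptoms occur and how long they last in each arm, and the schedule supports this well only up to 48 h. After that the full review stops until the last visit, although every child is due to be seen three times in between.

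The bowel effect deserves particular care. Section 6.2 says that relatedness cannot be established, because the infection and the antimalarials cause most of the listed symptoms too. Constipation is less affected by that difficulty. Sections 5.2 and 8.1 tie it to oAC. It is not among the malaria symptoms given as examples in 9.2, nor among the amodiaquine, artesunate or Coartem effects in 8.1. A comparison between arms is therefore easiest to interpret for this symptom, yet 6.2 does not name it, define it or say what will be done with the stool record.

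At stake is the completeness of the descriptive safety comparison. The non-inferiority decision on parasite half-life is not affected.

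**Working it through.** No sample size or power figure is involved. The check compares the schedules and the symptom lists.

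**1. Lists.** Collected (3.2, 7.1): nausea, vomiting, diarrhea, constipation, abdominal pain, headache, dizziness = 7. Named in 6.2: the same list without constipation = 6. The only difference is constipation.

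**2. Full symptom reviews.** Times: 0, 2, 4, 6, 8, 12, 18, 24, 30, 36, 42, 48 and about 168 h. The longest gap is 168 − 48 = 120 h. (Sections 7.1 and 9.3.1 and Table 3 all use 168 h. If Day 7 followed the numbering of Days 4-6, it would fall at 144 h and the gap would be 144 − 48 = 96 h.)

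**3. Bowel data.** Adding the stool records at 72, 96 and 120 h, the longest gap in any bowel information is 168 − 120 = 48 h.

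**4. Time since the last scheduled oAC dose (18 h).**

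| Contact | Hours after last dose | What is scheduled |
|---|---|---|
| 48 h | 48 − 18 = 30 | seven-symptom review |
| 72 h | 72 − 18 = 54 | stool passage only |
| 96 h | 96 − 18 = 78 | stool passage only |
| 120 h | 120 − 18 = 102 | stool passage only |
| 168 h | 168 − 18 = 150 | symptom review |

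If the 18 h dose is withheld, the last dose is at 12 h and each interval is 6 h longer.

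**5. What this does to frequency and duration.** A symptom present at 48 h and absent at 168 h ended somewhere in a 120 h window. A symptom that begins and ends inside the window is seen by no scheduled review. With reviews added at 72, 96 and 120 h, the windows become 24, 24, 24 and 48 h, so the longest falls from 120 to 48 h.

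**6. What the stool record can support.** It says whether stool was passed but not since when: since admission, since the last contact, or that day. No stool record is scheduled for 0-48 h, when constipation is only asked about as a symptom. The proportion with no stool since 0 h therefore cannot be derived with certainty at any time point.

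The row labels of Table 3 were not legible in the text available, so the check rests on the wording of 3.2 and 7.1.

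**The case against.** The strongest reply is that the protocol already follows the bowel effect over the relevant period. Stool passage is recorded about 54, 78 and 102 h after the last scheduled dose, and symptoms are reviewed again at about 150 h. This stands. A reader might infer that constipation is measured too early to be seen, but the stool record contradicts that. The documents also give no basis for saying when constipation becomes recognisable.

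A reader might also infer that constipation is left out of the analysis. The list in 6.2 is introduced as examples, so constipation is unnamed rather than excluded.

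The 120 h gap is 120/168 = 71% of follow-up. It would be wrong to read that as the share of bowel data that is missing, because it ignores the three stool records. Review also continues beyond 48 h if parasitemia persists, although 3.2 expects clearance by 48 h in all children.

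General adverse event questioning (9.2) and the documentation of adverse event outcomes at the last visit may catch some symptoms in the gap. This is a partial answer: 9.2 sets no times for the questioning. The case report form is not among the documents, so it is unknown whether start and stop times are captured.

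Finally, it is tempting to tie stool passage to amodiaquine absorption. Section 3.2 already addresses adsorption through the 54 h interval between the last oAC dose and the first amodiaquine dose, so that argument adds nothing here.

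**Conclusion.** The point holds in a limited form and is minor. The full symptom review has a 120 h gap that includes three contacts already in the schedule. Frequency and duration after 48 h are therefore poorly measured for an outcome listed as primary. Bowel function is partly covered by the stool record, but that record lacks a reference period, has no counterpart for 0-48 h, and has no planned summary.

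The silence of 6.2 on constipation is a missing detail and does not show an intention to omit it. The documents do not support a conclusion that the trial would fail to look for constipation when it might occur.

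The verdict assumes that parasitemia has cleared by 48 h, that the last visit is at about 168 h, and that the case report form adds no symptom review at 72-120 h beyond what 7.1 describes.

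**What to change.** **Section 7.1 and Table 3.** Repeat the existing seven-symptom review at the 72, 96 and 120 h contacts. Record stool passage from 0 h on the ward in both arms, and state the period to which each stool entry refers.

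**Section 6.2.** Name constipation among the symptoms. Tabulate by arm (a) reported constipation and (b) the proportion with no stool by 48, 72, 96 and 120 h. Because the trial is open-label, the stool record is a useful complement to reported constipation.

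**Cost.** A few minutes per child at contacts that already take place, slightly more data entry, and one further descriptive table. Sample size, treatment and the primary non-inferiority analysis do not change. If data collection is already over, the 6.2 change can still be made with the symptom and stool data in hand, with the unclear reference period stated as a limitation.

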6.3 Primary and Secondary Outcomes

6.3.1 Primary Outcome

- 1. To assess the safety of adjunct treatment with oAC
- 2. To compare parasite clearance half-life in patients treated with oAC + IV AS or IV AS

6.3.2 Secondary Outcomes

- 1. Serum cytokine levels at 0, 24, and 48 h
- 2. Whole-blood transcriptional profiles at 0, 24, and 48 h

7 STUDY PROCEDURES AND EVALUATION

7.1 Detailed Study Procedure Schedule

0 hours

- 1. Verify that informed consent was obtained.
- 2. Ensure that all inclusion/exclusion criteria are met.
- 3. Measure child's weight and vital signs: axillary temperature, blood pressure, heart and breathing rates, and state of consciousness.
- 4. Perform abbreviated history and physical examination and review for specific symptoms (i.e., nausea, vomiting, diarrhea, constipation, abdominal pain, headache, dizziness).
- 5. Place IV catheter in the arm.
- 6. Obtain 3 mL blood via IV catheter for research purposes: CBC with differential and platelet count, RNA preservation, and plasma preparation.
- 7. Prepare thick/thin blood films from finger-prick blood sample, count parasite density. Slide readers will be blinded to study participant's group allocation.
- 8. Administer AS 2.4 mg/kg IV to all children.
- 9. Administer a weight-based dose of Actidose Aqua® to children in the AS+oAC group, and a weight-based volume of clean water to children in the AS group.

2 hours (±10 min)

- 1. Prepare thick and thin blood films and count parasite density. Slide readers will be blinded to study participant's group allocation.
- 2. Measure vital signs, assess consciousness, and review specific symptoms (i.e., nausea, vomiting, diarrhea, constipation, abdominal pain, headache, dizziness).

4 hours (±10 min)

- 1. Prepare thick and thin blood films and count parasite density. Slide readers will be blinded to study participant's group allocation.
- 2. Measure vital signs, assess consciousness, and review specific symptoms. (i.e., nausea, vomiting, diarrhea, constipation, abdominal pain, headache, dizziness)

6 hours (±10 min)

- 1. Prepare thick and thin blood films and count parasite density. Slide readers will be blinded to study participant's group allocation.
- 2. Measure vital signs, assess consciousness, and review specific symptoms. (i.e., nausea, vomiting, diarrhea, constipation, abdominal pain, headache, dizziness)
- 3. Administer a weight-based dose of Actidose Aqua® to children in the AS+oAC group, and a weight-based volume of clean water to children in the AS group.

8 hours (±10 min)

- 1. Prepare thick and thin blood films and count parasite density. Slide readers will be blinded to study participant's group allocation.
- 2. Measure vital signs, assess consciousness, and review specific symptoms. (i.e., nausea, vomiting, diarrhea, constipation, abdominal pain, headache, dizziness)

12 hours (±10 min)

- 1. Prepare thick and thin blood films and count parasite density. Slide readers will be blinded to study participant's group allocation.
- 2. Inspect IV catheter.
- 3. Measure vital signs, assess consciousness, and review specific symptoms. (i.e., nausea, vomiting, diarrhea, constipation, abdominal pain, headache, dizziness).
- 4. Administer AS 2.4mg/kg IV to all children.
- 5. Administer a weight-based dose of Actidose Aqua® to children in the AS+oAC group, and a weight-based volume of clean water to children in the AS group.

18 hours (±45 min)

- 1. Prepare thick and thin blood films and count parasite density. Slide readers will be blinded to study participant's group allocation.
- 2. Measure vital signs, assess consciousness, and review specific symptoms. (i.e., nausea, vomiting, diarrhea, constipation, abdominal pain, headache, dizziness)
- 3. Identify the highest parasite density measured between 0 h and 12 h and divide it by the parasite density measured at 18 h. If this ratio is <2.0, complete the protocol as outlined below but do not administer the last dose of Actidose®-Aqua (for children in the AS+oAC group) or water (for control group), and do not draw venous blood at 24 h and 48 h (if the child is either in the AS or the AS+oAC group). Consider intensified clinical monitoring and an additional dose of 2.4 mg/kg AS IV for children with a ratio <2.0, if warranted by clinical signs and symptoms.

- 4. Administer a weight-based dose of Actidose Aqua® to children in the AS+oAC group and a weight-based volume of clean water to children in the AS group whose ratio of peak parasite density/18-h parasite density is ≥2.0 or if the 18-h parasitemia is zero.

24 hours (±10 min)

- 1. Prepare thick and thin blood films and count parasite density. Slide readers will be blinded to study participant's group allocation.
- 2. Inspect IV catheter.
- 3. Measure vital signs, assess consciousness, and review specific symptoms. (i.e., nausea, vomiting, diarrhea, constipation, abdominal pain, headache, dizziness)
- 4. Obtain 3 mL blood via IV catheter for research purposes.
- 5. Administer AS 2.4 mg/kg IV to all children.

30 hours (±10 min)

- 1. Prepare thick and thin blood films and count parasite density. Slide readers will be blinded to study participant's group allocation.
- 2. Measure vital signs, assess consciousness, and review specific symptoms. (i.e., nausea, vomiting, diarrhea, constipation, abdominal pain, headache, dizziness)

36 hours (±10 min)

- 1. Prepare thick and thin blood films and count parasite density. Slide readers will be blinded to study participant's group allocation.
- 2. Inspect IV catheter.
- 3. Measure vital signs, assess consciousness, and review specific symptoms. (i.e., nausea, vomiting, diarrhea, constipation, abdominal pain, headache, dizziness)

42 hours (±10 min)

- 1. Prepare thick and thin blood films and count parasite density. Slide readers will be blinded to study participant's group allocation.
- 2. Measure vital signs, assess consciousness, and review specific symptoms. (i.e., nausea, vomiting, diarrhea, constipation, abdominal pain, headache, dizziness)

48 hours (±10 min)

- 1. Prepare thick and thin blood films and count parasite density. Slide readers will be blinded to study participant's group allocation.
- 2. Inspect IV catheter.
- 3. Measure vital signs, assess consciousness, and review specific symptoms. (i.e., nausea, vomiting, diarrhea, constipation, abdominal pain, headache, dizziness)
- 4. Obtain 3 mL blood via IV catheter for research purposes.
- 5. Administer AS 2.4 mg/kg IV to all children.
- 6. Remove IV catheter.
- 7. If the parasitemia is undetectable, discharge participant from inpatient ward.

If parasitemia is detected at 48 h, we will retain the child as an inpatient, and continue preparing thick and thin blood films and counting parasite density until parasitemia is undetectable on thick smear in 6-hourly intervals.

Three age-based doses of AQ will be given orally on Days 4 (approx. 72 h), 5 (approx. 96 h), and 6 (approx. 120 h). On each day, we will record whether the child has passed stool.

On day 7 (approx. 168 h), we will follow up the participant to ensure (s)he is in good health. The site where the IV catheter was placed will be inspected, vital signs will be monitored, specific symptoms will be reviewed, and the outcome of any AE will be documented. At the discretion of the investigator, a focused clinical exam may be performed. A finger-prick blood sample will be

obtained from all children. If the child is healthy-appearing, the slide will be read at a later time. If the axillary temperature is >37.5°C, the slide will be examined immediately for malaria parasitemia. If the child is parasitemic, we will provide a full 3-day course of Coartem as directly-observed therapy. One day after the last dose of Coartem, we will take a finger-prick blood sample to document undetectable parasitemia.

168 hrs

х*

х

х

х

0 hrs	2 hrs	4 hrs	6 hrs	8 hrs	12 hrs	18 hrs	24 hrs	30 hrs	36 hrs	42 hrs	48 hrs	72 hrs	96 hrs	120 hrs
х														
х														
х														
					х		х		x		х			
х					х		х				х			
х			х		х	х								
												х	х	х
х	х	х	х	х	х	х	х	х	х	х	х			
						х								
х	х	х	х	х	х	х	х	х	х	х	х			
1.5							1.5				1.5			
1							1				1			
0.5							0.5				0.5			
ivated ch	arcoal a	rm only												
mia is un	detectal	ble												
blood pre	essure, r	espirato	ory rate,	state o	f consci	ousness	, and re	view of	specific	clinical	sympto	oms		
od collec	ted. In t	otal, 3 r	nls of bl	ood wil	l be coll	ected a	t 0, 24 a	nd 48hrs	5					
e in brac	kets													
* will be performed at the discretion of the investigator														
	0 hrs x x x x x x x x x x x ivated ch mia is un blood pre- od collect e in brack	0 hrs 2 hrs x x	0 hrs 2 hrs 4 hrs x x x x x <	0 hrs 2 hrs 4 hrs 6 hrs x - - - x - - - x - - - x - - - x - - - x - - - x - - - x x x x x x x x x x x x 1.5 - - 1.5 - - ivated charcoal arm only - mia is undetectable - blood pressure, respiratory rate, od collected. In total, 3 mls of blee in brackets investigator -	Ohrs 2 hrs 4 hrs 6 hrs 8 hrs x x x x x x x x x x x x x x x x x x x x x x x x x x x x x x x x x x x x x x x x x x x x x x x x x x x x x x x x x x x x 1.5	0 hrs 2 hrs 4 hrs 6 hrs 8 hrs 12 hrs x x x x x	0 hrs 2 hrs 4 hrs 6 hrs 8 hrs 12 hrs 18 hrs x x x	O hrs 2 hrs 4 hrs 6 hrs 8 hrs 12 hrs 18 hrs 24 hrs x 24 hrs x	0 hrs 2 hrs 4 hrs 6 hrs 8 hrs 12 hrs 18 hrs 24 hrs 30 hrs x x x x x	0 hrs 2 hrs 4 hrs 6 hrs 8 hrs 12 hrs 18 hrs 24 hrs 30 hrs 36 hrs x x x x	Ohrs 2 hrs 4 hrs 6 hrs 8 hrs 12 hrs 18 hrs 24 hrs 30 hrs 36 hrs 42 hrs x 30 hrs 36 hrs 42 hrs x 30 hrs 36 hrs 42 hrs x x x<	Ohrs 2 hrs 4 hrs 6 hrs 8 hrs 12 hrs 18 hrs 24 hrs 30 hrs 36 hrs 42 hrs 48 hrs x	Ohrs 2 hrs 4 hrs 6 hrs 8 hrs 12 hrs 18 hrs 24 hrs 30 hrs 36 hrs 42 hrs 48 hrs 72 hrs x Ohrs 2 hrs 4 hrs 6 hrs 8 hrs 12 hrs 18 hrs 24 hrs 30 hrs 36 hrs 42 hrs 48 hrs 72 hrs 96 hrs x 	Ohrs 2 hrs 4 hrs 6 hrs 8 hrs 12 hrs 18 hrs 24 hrs 30 hrs 36 hrs 42 hrs 48 hrs 72 hrs 96 hrs x

A summary of study procedures is shown in Table 3.

Table 3: Summary of study procedures

